## **Malignancy**

19. History or presence of malignancy (except for surgically excised and non-recurrent cutaneous basal cell carcinoma, squamous cell carcinoma, or cervical carcinoma), lymphoproliferative disease, or history of total lymphoid irradiation within 10 years prior to Screening.

## **Transplantation**

20. History or presence of homologous (allogenic) bone marrow or solid organ transplantation.

## **Ophthalmologic**

21. Presence of macular edema or active uveitis detected by OCT during Screening.

## **Metabolic**

22. Documented poorly controlled diabetes mellitus (i.e., HbA1c > 8.0% at Screening as reported by the central laboratory or unstable blood sugar control/treatment adherence as per investigator's judgment) or diabetes mellitus complicated with organ involvement, such as diabetic nephropathy or retinopathy as assessed by investigator.

## **Hepatic**

23. History of chronic liver or biliary disease (other than Gilbert's Syndrome) or participants with ALT or AST > 3 × ULN or TBIL > 1.5 × ULN (unless in the context of known Gilbert's Syndrome).

## **Hematology**

24. Significant hematology abnormality at screening assessment:

- Lymphocyte count < 500 / $\mu$ L ( $0.5 \times 10^9$ /L);
- Hemoglobin < 7 g/dL;
- WBC count < 2000/ $\mu$ L ( $2.0 \times 10^9$ /L) or
- Platelets < 25,000/ $\mu$ L ( $25 \times 10^9$ /L).

## **Renal**

25. eGFR < 15 mL/min/1.73 m^2.

## **Medications**

26. Treatment with the following medications within 15 days or 5 half-lives of the medication (whichever is longer) prior to Day 1:

- $\beta$ -blockers, diltiazem, verapamil, digoxin, digitoxin, or any other anti-arrhythmic or HR-lowering systemic therapy [list of drugs provided in Appendix 3].

- QT-prolonging drugs with known risk of torsade de pointes irrespective of indication [list of drugs provided in Appendix 4].

27. Treatment with the following medications within 30 days or 5 half-lives of the medication (whichever is longer) prior to Day 1:

- Cyclophosphamide, cyclosporine, voclosporin, tacrolimus, sirolimus, etc.
- Pulse methylprednisolone.
- Vaccination with live vaccines.

28. Intra-articular, intramuscular, or i.v. CS within 6 weeks prior to Day 1.

29. Treatment with the following medications within 90 days or 5 half-lives of the medication (whichever is longer) prior to Day 1:

- Leflunomide.
- i.v. immunoglobulins.

30. Treatment with any investigational agent within 90 days or 5 half-lives of the drug (whichever is longer) prior to Day 1.

31. Treatment with B cell-depleting biological agents (e.g., rituximab or ocrelizumab) or biological immunosuppressive agents (e.g., anti-TNF, anti-IL1, anti-IL6 therapies) within 12 months prior to Day 1.

32. Treatment with anifrolumab within 6 months prior to Day 1.

33. Treatment with any of the following medications any time prior to Screening:

- Alemtuzumab.
- S1P receptor modulators (e.g., fingolimod).
- Participants previously randomized to cenerimod or placebo in any trial involving cenerimod.

### **Other categories**

34. Recent clinically significant drug or alcohol abuse as per investigator's judgment.

35. Known allergy to S1P receptor modulators or any of the cenerimod formulation excipients.

36. Any other clinically relevant medical condition that would put the participant at risk if participating in the study, or any other diseases that may confound the disease activity assessments.

37. Participants with body weight < 40 kg at Screening or Day 1.

## 5.4 Rationale for the selection of the study population

The target population of this study is similar to the participant population from the Phase 2b ID-064A202 study as it consists of adult participants with generalized SLE who are receiving background therapy.

Participants must have at least a 6-month history of SLE and must be classified as SLE according to 2019 EULAR/ACR criteria [Aringer 2019]. This study is being performed in patients with SLE in order to evaluate the PK and PD effects in the target population which may benefit from cenerimod. Healthy volunteers would not allow for the same evaluation, as for example lymphopenia is often more prevalent in SLE as compared to healthy people.

Participants will be included in the study if they have a sufficient level of disease activity to justify therapeutic intervention.

However, since only limited efficacy data are available to date, it is premature to test cenerimod in the most severe spectrum of the disease. In line with our exclusion criteria, participants with active lupus nephritis and CNS lupus requiring additional immunosuppressive therapies are excluded [see Section 5.3].

Given the heterogeneity in SLE disease manifestations, treatment is often not standardized. In order not to confound the results of the study, participants should have initiated SLE background treatment (except OCS) at least 3 months prior to Screening and need to have stable doses at least 30 days prior to Day 1 and throughout the study. Background OCS therapy should have been initiated at least 30 days prior to Screening and the dose must be stable at least 15 days prior to Day 1 [see Section 5.2 and 6.2.1.2]. The inclusion of participants with background therapies commonly used to treat SLE in China will allow the evaluation of safety in a smaller number of patients prior to starting a large clinical study in China.

## 5.5 Contraception requirements for women of childbearing potential

### 5.5.1 Definition of childbearing potential

A woman is considered to be of childbearing potential, i.e., fertile, following menarche and until becoming post-menopausal unless permanently sterile.

Permanent sterilization methods include hysterectomy, bilateral salpingectomy, and bilateral oophorectomy.

Post-menopausal state is defined as 12 consecutive months with no menses without an alternative medical cause (ICH M3 definition).

### 5.5.2 Methods of contraception

Cenerimod is embryotoxic and teratogenic in animal studies. WoCBP [see definition in Section 5.5.1] must use an **uninterrupted highly effective** method of contraception from Screening (Visit 1) up to at least 6 months after study treatment discontinuation due to the long half-life of the study treatment (33 days).

Contraceptive methods with low user dependency should preferably be used, in particular when contraception is introduced as a result of participation in the study.

Highly effective methods of contraception are defined as those, alone or in combination, resulting in a failure rate of < 1% per year when used consistently and correctly. Such methods include:

- Hormonal contraceptives: Combined (containing estrogen and progestogen) or progestogen-only hormonal contraception associated with inhibition of ovulation using one of the following routes of administration:
  - Oral
  - Intravaginal
  - Transdermal
  - Injectable
  - Implantable (low user dependency)

If a hormonal contraceptive is chosen from this group, it must be taken for at least 30 days prior to administration of the first study treatment dose. If, during the study treatment period, a participant switches or starts a hormonal contraceptive method, caution must be taken to ensure a highly effective method of contraception is used without discontinuation in order to ensure continued effective contraception.

- Intrauterine device (low user dependency).
- Intrauterine hormone-releasing system (low user dependency).
- Bilateral tubal occlusion/ligation at least 6 weeks prior to Screening (low user dependency).
- Vasectomized partner: this is a highly effective birth control method, provided that the partner is the sole sexual partner of the participant and that the vasectomized partner has received a medical assessment of the surgical success.
- Sexual abstinence, defined as refraining from heterosexual intercourse during the entire period of risk associated with the study treatment. The reliability of sexual abstinence needs to be evaluated in relation to the duration of the clinical study; whether it is the preferred and usual lifestyle of the participant; and whether it is locally accepted as a highly effective method of contraception.

The following contraception schemes **used alone** are NOT considered highly effective methods of contraception:

- Male or female condom with or without spermicide.
- Cap, diaphragm, or sponge with or without spermicide.

The following methods are not allowed as methods of contraception for this study:

- Progestogen-only oral hormonal contraception (except if inhibition of ovulation is the primary mode of action).
- Periodic abstinence (calendar, symptothermal, post-ovulation methods).
- Withdrawal (coitus interruptus).
- Spermicides only.
- Lactational amenorrhea method.
- Combination of female condom and male condom.

The methods of birth control used (including non-pharmacological methods) of the WoCBP and/or partner (if applicable) must be recorded in the eCRF.

The investigator must explain and remind female participants of the importance of using methods of contraception **at every study visit**.

The investigator/delegate will record in the eCRF at monthly intervals the result of the pregnancy test, whether the method of contraception has changed, and will remind the participant to follow the protocol-mandated method of contraception up to at least 6 months after study treatment discontinuation.

If the investigator/delegate finds that the protocol-mandated highly effective method of contraception is not consistently and correctly followed by the participant, the study treatment **must** be permanently discontinued [see Section 5.8.1.3].

Note: The documentation of the methods of contraception can be based on the site personnel's review of the participant's medical records, medical examination, or medical history interview of the participant.

## **5.6 Contraception for male participants with a partner who is of childbearing potential**

Cenerimod is neither genotoxic nor mutagenic [see section 4.3.8.7 of the Cenerimod IB]. Thus, no contraceptive methods are needed for male participants participating in this clinical study. Based on nonclinical data and human distribution models, it is considered very unlikely that a relevant dose of cenerimod would be delivered to the female by seminal

fluid transfer. Therefore, despite the teratogenic effect of cenerimod, the risk of harm to a human fetus by seminal transfer of cenerimod is very low.

## 5.7 Screen failures and re-screening

Screen failures are defined as participants recruited in the clinical study (i.e., ICF fully signed) who are not subsequently enrolled in the study. Participants may have a laboratory assessment repeated once during the screening period, if, in the investigator's medical opinion, the value leading to ineligibility is transient and not clinically significant, prior to the participant being screen failed.

A minimal set of screening failure information is required to ensure compliant reporting of screening failure participants. For participants who failed Screening, the following data will be recorded in the eCRF:

- ICF signature date;
- Age, sex, and race;
- Inclusion criteria not met and/or exclusion criteria met;
- SAEs.

Re-screening of participants after screen failure is not allowed.

## 5.8 Criteria for withdrawal of participants

A participant has the right to permanently discontinue the study treatment at any time by withdrawing from the study treatment only or by withdrawing from the study treatment **and** any further participation in the study (i.e., premature withdrawal from the study). It is recommended that the investigator/delegate makes a reasonable effort to maintain participants on treatment, as medically appropriate, and follow the schedule of visits, as data robustness depends on such compliance. Should a participant stop treatment or withdraw from the study, the investigator/delegate should ascertain the reason(s), while fully respecting the participant's rights.

### 5.8.1 Study treatment interruption and permanent discontinuation of study treatment

#### 5.8.1.1 Principles

The decision to permanently discontinue the study treatment can be made by the participant, the investigator/delegate, or the sponsor personnel.

The investigator/delegate has the option of temporarily interrupting or permanently discontinuing the study treatment for a given participant in response to an AE, a diagnostic or therapeutic procedure, a laboratory abnormality, or for administrative reasons. If the

study treatment is interrupted by the participant for any reason, he/she must inform the investigator/delegate as soon as possible. Any study treatment interruptions (i.e., for a day or more) must be recorded in the eCRF.

The investigator/delegate must permanently discontinue the study treatment for a given participant if, on balance, he/she believes that continued administration would be contrary to the best interests of the participant.

Study-specific criteria for temporary interruption and permanent discontinuation of the study treatment are described in Sections 5.8.1.2 to 5.8.1.11.

The main reason for permanent discontinuation of the study treatment (e.g., due to pre-specified study treatment discontinuation criteria, an AE, lack of efficacy, study termination) must be documented in the eCRF.

A participant who permanently discontinues the study treatment is **NOT** considered withdrawn from the study. The participant will be asked to return for a pEOT visit within 7 days after the last dose of study treatment intake, and thereafter to attend further planned visits as defined in the SoA [Table 2 and Table 3] and in Section 7.2.

All participants withdrawn from study treatment are encouraged to continue the planned study procedures (e.g., visits and questionnaire completion [Table 3]) until planned FSV, provided that the participant's consent for this further limited participation in the study has not been withdrawn. This will decrease the amount of missing data, which is important to maintain the integrity of the study.

### **5.8.1.2 *Pregnancy***

If a participant becomes pregnant while on study treatment, the study treatment **must** be permanently discontinued. The investigator/delegate must counsel the participant and discuss the risks of continuing with the pregnancy and the possible effects on the fetus. For reporting of pregnancies, refer to Section 8.3.1.

If a participant has a positive urine pregnancy test, the study treatment must be interrupted immediately. A serum pregnancy test must be performed as soon as possible. If the pregnancy is confirmed, the study treatment **must** be permanently discontinued. If the result of the serum pregnancy test is negative, the study treatment may be resumed.

### **5.8.1.3 *Lack of compliance with methods of contraception***

If the investigator/delegate considers that the participant is not compliant with the protocol methods of contraception instructions, the study treatment **must** be permanently discontinued.

### **5.8.1.4 *Cardiovascular***

All clinically relevant ECG or vital sign abnormalities as per investigator's judgment must be recorded as an AE in the eCRF as per protocol AE definitions [see Section 8.1.1].

#### *5.8.1.4.1 Day 1 specific stopping criteria*

Cardiac monitoring on the first dose on Day 1 and on the first day of re-initiation of study treatment will be required for participants.

Participants **must** be permanently discontinued from study treatment if any of the following occurred on Day 1 or on the day of re-initiation:

- HR < 40 bpm at two consecutive hourly 12-lead ECG post-dose assessments;
- SBP < 90 mmHg at two consecutive hourly BP measurements post-dose;
- For participants with baseline pre-dose SBP < 90 mmHg: decrease in SBP of > 5 mmHg from pre-dose SBP value at two consecutive hourly BP measurements post-dose;
- The participant does not meet the criteria for discharge from the monitored setting at 12-hour post-dose.

Close monitoring (ECG or BP, as appropriate) is recommended for participants who meet study treatment discontinuation criteria as detailed in Appendix 5.

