 The post dose 12-lead ECGs assessments will be measured once at each hourly time point within 12 hours post-dose, while SBP/DBP assessments will be measured once at each hourly time point within 6 hours post-dose and at 12 hours post-dose at Visit 2 (Day 1) and at study treatment re-initiation. At the 12-hour post-dose timepoint, participants may be discharged from the monitored setting if they meet the pre-specified discharge criteria. For discharge criteria see Appendix 5.

 Physical examination will only be performed at Visits 1, 2, 3, 5, 8, 11, 14, and 15. For all other visits, a symptom-driven abbreviated physical examination will be performed to capture assessments needed for the SLEDAI-2K, the PGA, the BILAG, the CLASI and the SFI.

 Body weight (measured under fasting conditions in the morning) should be recorded in the BILAG assessment page in the paper sheets at all visits in which this assessment is performed. It should also be recorded in the eCRF at Visits 1, 14, and 20.

 At all visits, a single pre-dose 12-lead ECG will be performed and transmitted to the central reader. A pre-dose SBP/DBP will be performed at all visits (including Screening) in duplicate and both values, including the arm and position used, will be entered into the eCRF.

 Aldolase to be measured only at investigator's request.

 A central laboratory will be used for all protocol-mandated laboratory tests, including retests due to laboratory abnormalities and laboratory tests performed at unscheduled visits. Local laboratory tests may be required under exceptional circumstances and results should be recorded as unscheduled local laboratory in eCRF.

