#### *7.2.3.3.2 Additional cardiac monitoring on Day 1*

To evaluate the possible transient effects on BP and HR after study treatment initiation with S1P receptor modulators, 12-lead ECGs and BP assessments will be additionally performed as post-dose cardiac monitoring for all participants on Day 1 and at study treatment re-initiation visit(s).

The post-dose cardiac monitoring will consist of post-dose 12-lead ECGs, performed hourly within 12 hours post dose, and BP assessments, performed hourly within 6 hours post dose and at 12 hours post dose as per the SoA. At 12 hours the participant may be discharged from monitored setting if they meet the discharge criteria [see Appendix 5] If the participant does not meet the discharge criteria at 12 h post-dose, the participant will be permanently discontinued from the study treatment and will be kept in the monitored setting for observation.

Any cardiac events of potential clinical concern on Day 1 and on the first day of re-initiation visit must be assessed by the investigator or their delegate for seriousness. In addition, the investigator or their delegate should determine the need for medical management and decide what actions should be taken on study treatment, if any. The investigator or their delegate may consult with a cardiologist. In cases of acute cardiac events, and if they are not adequately trained and experienced in cardiology and are not equipped to provide emergency treatment, she/he will refer the participant to a cardiologist to receive emergency care and treatment.

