## **Appendix 5 Criteria for discharge from monitored setting on Day 1 and on the first day of re-initiation following treatment interruptions**

At the 12 hours post-dose on Day 1 and on the first day of re-initiation of study treatment following treatment interruptions lasting for at least 7 days in the first 14 days of treatment, all the following criteria must be met:

- ECG-derived resting HR > 45 bpm; *and* if HR < 50 bpm it must not be the lowest value measured post-dose;
- SBP  $\geq$  90 mmHg;
- For participants with baseline pre-dose SBP < 90 mmHg: decrease in SBP of  $\leq$  5 mmHg from pre-dose SBP value;
- QTcF < 500 ms (females) or < 480 ms (males);
- No newly occurred persistent clinically significant ECG abnormality (e.g., AV block second-degree or higher) or ongoing AE requiring continued hospitalization;
- No other clinically significant symptoms, signs or abnormalities as per judgment of the investigator.

If at 12 h post-dose the participant does not meet discharge criteria, he/she must be permanently discontinued from study treatment. Participants who are permanently discontinued should not be discharged from the monitored setting before the HR abnormalities and BP return to near baseline values and until there are no persistent ECG abnormalities (e.g., AV block second-degree or higher) or ongoing AE requiring continued hospitalization, or until a diagnosis is established.

Discharge criteria will be recorded in the eCRF.

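### Day 1 SBP stopping and discharge rules: the separate criterion for pre-dose SBP below 90 mmHg can never change the outcome, so unchanged low SBP forces permanent discontinuation

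*Combined protocol and SAP*

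**What the plan says.** Section 5.8.1.4.1 says participants must "be permanently discontinued from study treatment if any of the following occurred on Day 1 or on the day of re-initiation". Two of the items concern systolic pressure:

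- "SBP < 90 mmHg at two consecutive hourly BP measurements post-dose", for every participant.
- "For participants with baseline pre-dose SBP < 90 mmHg: decrease in SBP of > 5 mmHg from pre-dose SBP value", again at two consecutive hourly readings.

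A further item in that list is failure to meet the discharge criteria at 12 h. Those criteria are in Appendix 5, where "all the following criteria must be met". They include SBP of at least 90 mmHg, again for every participant. The next line begins "For participants with baseline pre-dose SBP < 90 mmHg: decrease in SBP of" and allows a fall of no more than 5 mmHg.

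Appendix 5 then states: "If at 12 h post-dose the participant does not meet discharge criteria, he/she must be permanently discontinued from study treatment". Section 7.2.3.3.2 repeats the consequence: "If the participant does not meet the discharge criteria at 12 h post-dose, the participant will be permanently discontinued from the study treatment".

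On timing, Table 2 footnote 1 says "SBP/DBP assessments will be measured once at each hourly time point within 6 hours post-dose and at 12 hours post-dose".

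**The concern.** Both lists carry a line written for participants who start below 90 mmHg, with a 5 mmHg tolerance. Neither list limits the general 90 mmHg criterion to participants who start at or above 90. Neither says whether the subgroup line replaces that criterion or adds to it. Section 5.8.1.7 shows the protocol can separate subgroups explicitly: it gives one INR threshold for participants not on an anticoagulant and another for those who are.

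The subgroup can enroll. Cardiovascular exclusions 7 to 10 in section 5.3 set heart rate and QTcF limits but no SBP floor.

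The stop is mandatory, and section 10.7 does not permit waivers. A site that reads the list literally stops a participant whose low SBP has not moved, while a site that treats the subgroup line as a replacement continues the same participant. The literal reading errs towards extra stopping, not unsafe continuation.

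The Day 1 summaries in section 9.2.1 depend on the reading used: discharge at 12 h, reasons for non-discharge, and discontinuation after 12 h. A participant stopped on Day 1 has no Month 2 dosing interval and no accumulation index, and PK is a primary objective. Section 7.1.1 counts a participant towards the enrollment target once Day 1 is completed and cenerimod received, and no replacement rule is stated.

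**Working it through.** The plan gives no figure to reproduce. The check is logical, followed by an illustration of size.

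**1. Stopping list (any item suffices).** Let b be pre-dose SBP, with b < 90. A fall of more than 5 means SBP < b − 5 < 85, hence SBP < 90. Every pair of readings that meets the subgroup item therefore already meets the general item. Enumeration over integer pre-dose values 60 to 160 and two post-dose readings each from 50 to 170 gives 101 × 121 × 121 = 1,478,741 combinations. The subgroup item changed the outcome in 0.

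**2. Discharge list (all items needed).** If b < 90 and SBP at 12 h is at least 90, SBP has risen, so a fall of 5 or less is automatic. Over 101 × 121 = 12,221 combinations, the subgroup item changed the outcome in 0.

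**3. Forced stops with no fall.** There were 9,455 combinations with pre-dose below 90, both readings below 90 and neither reading lower than pre-dose. All 9,455 force a stop. Examples:

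| Pre-dose | Two readings | Literal | Subgroup line replaces |
|---|---|---|---|
| 88 | 88, 88 | stop | continue |
| 86 | 89, 89 | stop | continue |
| 88 | 82, 82 | stop | stop |

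A participant at 89 before dosing and 91 afterwards is not stopped under either reading.

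**4. Where the two readings of the text differ.** They differ for post-dose SBP from b − 5 to 89: 84–89 for b = 89, 83–89 for b = 88, 80–89 for b = 85, and 75–89 for b = 80.

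**5. Illustrative probability of a mandatory SBP stop.** The inputs are b = 88; true mean after dosing also 88 (assumed); single-reading SD of 3, 5 or 8 mmHg (assumed); values rounded to integers; readings at hours 1 to 6 and 12. Section 2.4.4 reports no consistent SBP change over time in the Phase 2b study, but those are not Day 1 data. A stop occurs if any of the 5 consecutive pairs in hours 1 to 6 meets the criterion, or if the 12 h reading does.

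With independent readings and per-reading probability p, the chance of no qualifying pair in six readings is N = Σ C(7−k, k) p^k (1−p)^(6−k), k = 0 to 3. Then P(stop) = 1 − N(1−p).

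For SD 5:

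- Literal: p = Φ((89.5 − 88)/5) = 0.618, N = 0.167, P = 1 − 0.167 × 0.382 = 0.936.
- Replacement: p = Φ((82.5 − 88)/5) = 0.136, N = 0.919, P = 1 − 0.919 × 0.864 = 0.206.

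The results with correlation 0.5 between readings (assumed) come from 400,000 simulated draws.

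| SD | Literal, independent | Replacement, independent | Literal, corr. 0.5 | Replacement, corr. 0.5 |
|---|---|---|---|---|
| 3 | 97% | 4% | 87% | 5% |
| 5 | 94% | 21% | 81% | 21% |
| 8 | 91% | 42% | 77% | 38% |

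**6. How many participants.** The documents do not say how common pre-dose SBP below 90 is. For an assumed 1%, 2% or 5%, the expected number among 15 is 0.15, 0.30 or 0.75. The chance of at least one, 1 − (1 − p)^15 with p now that proportion, is 14%, 26% or 54%. Each Day 1 stop removes 1/15 = 6.7% of the Month 2 PK and accumulation data.

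**The case against.** The best counter-argument is that a sensible reader will see what is meant. The subgroup line directly follows the general one and does nothing unless it replaces it, so this is a missing qualifier. That may well be how some sites read it, but the text does not say so, and a mandatory stop should not depend on inference.

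The affected group may also be empty, the error is towards caution, the analyses are descriptive, and loss of Month 2 data follows from any Day 1 stop. All of this stands and limits the weight of the point. Exclusion 36 lets an investigator exclude on judgment but sets no SBP limit.

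The probabilities in step 5 are open to challenge because they set the true mean equal to the observed 88. Someone identified by one low reading will tend to have a higher true SBP. Assume a population mean of 115, a between-person SD of 12 and an observed pre-dose value of 88 as the mean of two readings. For SD 3, 5 and 8 the literal stop probability is then about 81%, 69% and 57%, against 6%, 16% and 22% under replacement. The gap narrows, to about 36 points at SD 8, but remains large.

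Finally, *never* assumes one pre-dose value. At re-initiation, if baseline meant the Day 1 value and pre-dose that day's value, the subgroup item could fire alone: Day 1 baseline 88, re-initiation pre-dose 120, readings 110 and 110. That is a strained reading and does not touch Day 1.

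**Conclusion.** The concern holds. As written, the subgroup SBP criterion is inert in both lists, and a participant who starts and stays below 90 mmHg must be permanently discontinued even if SBP is unchanged or rises. The logic needs no distributional assumption, only that baseline and pre-dose SBP are the same number.

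The size per affected participant rests on assumed SDs, correlation and mean. Across the scenarios examined, including the higher-true-SBP case, a literal stop has probability 57% to 97%, against 4% to 42% under replacement. The expected number affected is below one for assumed prevalences up to 5%, and may be zero. This should be fixed before enrollment, but it is not a threat to participant safety or to the trial as a whole.

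**What to change.** Reconcile section 5.8.1.4.1 and Appendix 5 so that each list states which SBP criterion applies to which pre-dose SBP, and whether the subgroup line replaces the 90 mmHg criterion or adds to it. Make the eCRF discharge-criteria page match; that page is not in the documents, so whether it already settles the point cannot be checked. Which rule applies is a decision for the sponsor's medical team.

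The same wording should name the pre-dose value. Section 7.2.4 takes two readings and computes their mean, while section 3.1 defines baseline as the last available measurement. Readings of 94 then 88 give (94 + 88)/2 = 91 on one definition and 88 on the other. This has no effect on Day 1 while the criterion is inert, but it decides who falls under it once it operates. State also which day's value is used at re-initiation.

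The cost is wording in two places and one eCRF page at the next amendment. The amendment details for V3.0 report no participants enrolled, so no data would be affected if this is done before the first dose.
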